## 6. TREATMENT(S)

The non-radiolabelled IMP will be supplied to the clinical site under the responsibility of the Sponsor, who will also provide the Pharmacist/Investigator with appropriate certificates of analytical conformity and QP release.

The radiolabelled Drug substance (DS) will be provided by [REDACTED], [REDACTED] will manufacture the Drug Product (DP) for IV infusion, it will be manufactured and Certified by a [REDACTED] QP and supply straight to the clinic.

The analytical and microbiological methods related to the radiolabelling procedure will be validated and reports will be generated.

### 6.1 [REDACTED]

#### CHF6001 800µg/20mg NEXThaler® DPI

- *Active ingredient:* CHF6001
- [REDACTED]
- [REDACTED]
- [REDACTED]

#### CHF6001 DPI NEXThaler® matched placebo (for Training kit)

- *Active ingredient:* None
- [REDACTED]
- [REDACTED]
- [REDACTED]

Clinical Study Code: CLI-06001AA1-02	Version No.: 1.0
EUDRACT No.: 2020-004201-31	Date: 19 October 2020

**[C]-CHF6001 1,85µg/ml (50nCi/ml) solution for IV infusion**

- *Active ingredient:* [C]-CHF6001
- *Formulation vehicle:* ethanol and kolliphor®HS 15 in 0.9% w/v saline
- *Appearance:* clear and colourless solution in a glass vial

## **6.2 Dosage and Administration**

### **6.2.1 Selection of doses in the study**

#### **Inhaled dose**

The highest CHF6001 dose planned to be tested in the Phase 3 program studies is 1600µg administered twice-daily corresponding to a total daily dose of 3200µg.

CHF6001 is mainly metabolized to CHF5656 and CHF6095, which are detected in the circulation of COPD patients at concentrations approximately 20- and 50- fold lower, respectively, than the parent compound CHF6001. CHF5956, the major metabolite of CHF6001, was 2,000-fold less potent than the parent compound in an in vitro model of LPS-induced TNF-alpha production in human isolated peripheral blood mononuclear cells.

Therefore, this clinical trial was designed taking into consideration the linear and time-independent PK at concentrations found to be safe and well tolerated in healthy subjects and patients for the active parent compound CHF6001. For this reason, mass balance characterization of CHF6001 after single dose administration of 3200µg is deemed appropriate.

#### **Intravenous dose**

The proposed intravenous dose of 18.5µg (given over a 15-minutes infusion) accounts for less than 0.6% of the concomitant cold inhaled dose (3200µg). The overall dose (3218.5µg) is therefore expected to be well within the highest dose tested in humans (4800µg by inhalation).

The radioactive dose will be approximately 500nCi. The radioactive burden is considered to pose negligible additional risk above the background cosmic radiation, so no dosimetry estimation is necessary.

Clinical Study Code: CLI-06001AA1-02	Version No.: 1.0
EUDRACT No.: 2020-004201-31	Date: 19 October 2020

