### *[ $^{14}\text{C}$ ]-CHF6001 IV infusion:*

- Detailed information on the process for formulation preparation are in the pharmacy protocol. The IV formulation will be administered intravenously as a single dose over 15 minutes, ending at the expected  $T_{\text{max}}$  of 2 h for the inhaled dose giving a total infused dose of 18.5 $\mu$ g and 500nCi (18.5kBq).

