## 7. STUDY PLAN

### 7.1 Study Schedule

	Screening	Treatment Period				Follow-up
		Day -1	Day 1	Day 2-10	Day 11	
Informed consent	X					
Residential period		X	X	X		
Discharge					X	
Treatment intake						
IMP administration				X 		
Training						
Training with In-Check Dial	X	X	X			
Training with Placebo	X	X	X			
Subject Health Evaluation						
In/Ex Criteria	X	X				
Medical History	X					
Demographic data	X					
Height and weight	X					
Alcohol breath test	X	X				
Physical examination	X	X			X 	
Adverse Events recording	X	X	X	X	X	X
Restrictions	X	X	X	X	X	
Concomitant Med	X	X	X	X	X	X
Safety assessment in blood						
Clinical Chemistry	X				X 	
Serology	X					
Haematology	X				X 	
Fasting glucose	X				X 	
Generic assessments in urine						
Urinalysis	X					
Drug panel	X	X				
Cotinine	X	X				
Samples for PK evaluations a						
Blood			X	X	X	
Urine		X	X	X	X	

Clinical Study Code: CLI-06001AA1-02	Version No.: 1.0
EUDRACT No.: 2020-004201-31	Date: 19 October 2020

	Screening	Treatment Period				Follow-up
		Day -1	Day 1	Day 2-10	Day 11	
Feces		X	X	X	X	
Cardiac assessmentsb						
Local ECG	X		X			
Vital Signs - Blood Pressure	X		X			
Pulmonary Assessment						
Spirometry	X					

Footnotes for Evaluation Schedule:

1. There will be 2 types of administration:
  - 4 inhalations of CHF6001 800 $\mu$ g/20mg DPI NEXThaler®
  - Intravenous infusion for 15min of the tracer starting 1h45min after the inhaled dose (time of the first inhalation) and ending at the expected  $T_{max}$  of 2 h for the inhaled dose
2. A full physical examination and collection of blood safety test will be performed at discharge. A follow-up visit will be done only if deemed necessary by the principal investigator.

a) Pharmacokinetic samples will be collected as:

- **Blood samples** for plasma non-radiolabeled CHF6001 to be collected at pre-dose (within 60 min from inhaled dosing) and at the following timepoints post inhaled dose: **15, 30, 60, 90 min, 2, 3.75, 5.75, 7.75, 9.75, 11.75, 13.75, 25.75, 49.75, 73.75, 97.75, 121.75, 145.75, 169.75, 193.75, 217.75 and 241.75 hours.**

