#### 7.2.1.1 Determination of CHF6001 and related analytes in human plasma

Blood samples for the determination of plasma total [C], [C]-CHF6001, metabolite profiling (if required) and non-radiolabeled CHF6001, will be collected and processed according to an established laboratory manual at pre-dose and in the 0-240h interval after dosing, as follows:

- 22 blood samples of 4 mL for plasma non-radiolabeled CHF6001 will be collected at pre-dose (within 60 min from inhaled dosing) and at the following timepoints post inhaled dose: 15, 30, 60, 90 min, 2, 3.75, 5.75, 7.75, 9.75, 11.75, 13.75, 25.75, 49.75, 73.75, 97.75, 121.75, 145.75, 169.75, 193.75, 217.75 and 241.75 hours;
- 25 blood samples of 5 mL for plasma total [C] and [C]-CHF6001 will be collected at pre-dose (within 60 min from inhaled dosing) and at the following timepoints relative to the start of the IV infusion: 5, 10, 15 [end of infusion], 20, 25, 30, 45, 60 min, 2, 4, 6, 8, 10, 12, 24, 48, 72, 96, 120, 144, 168, 192, 216 and 240 hours;
- 25 blood samples of 10 mL for plasma [C] of the relevant metabolites will be collected at pre-dose (within 60 min from inhaled dosing) and at the following timepoints relative to the start of the IV infusion: 5, 10, 15 [end of infusion], 20, 25, 30, 45, 60 min, 2, 4, 6, 8, 10, 12, 24, 48, 72, 96, 120, 144, 168, 192, 216 and 240 hours;
- 2 blood samples of 2 mL for whole blood total [C] and [C]-CHF6001 will be collected at pre-dose (within 60 min from inhaled dosing) and 20 min after the start of infusion (for a total of 4 samples).

The processing, storage and shipment of samples are detailed in the laboratory manual document.

Day	Clock time (exemplary)	Time after inhaled administration	Time after start of i.v. administration	Time deviation allowed	PK timepoint inhaled administration	PK timepoint i.v. administration
1	08:00	Pre-dose		Within 60 minutes from inhalation	X 	X 

Clinical Study Code: CLI-06001AA1-02	Version No.: 1.0
EUDRACT No.: 2020-004201-31	Date: 19 October 2020

	09:00	Start of inhaled administration			
	09:15	15 min	± 2 min	X 	
	09:30	30 min	± 2 min	X 	
	10:00	60 min	± 5 min	X 	
	10:30	90 min	± 5 min	X 	
	10:45		Start of infusion (SOI)		
	10:50		SOI + 5 min	± 2 min	X 
	10:55		SOI + 10 min	± 2 min	X 

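### Unlabelled drug in the IV tracer dose is counted as inhaled drug, so F_inh is biased upward by a small amount that matters mainly if F_inh is low

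*Protocol*

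**What the plan says.** **Doses.** Protocol 6.2.1 (Intravenous dose) sets 18.5 µg for the tracer and 3200 µg by inhalation, and remarks that the former "accounts for less than 0.6% of the concomitant cold inhaled dose". Their sum, 3218.5 µg, is then compared with the highest dose already tested in humans. On activity: "The radioactive dose will be approximately 500nCi", given elsewhere as 18.5 kBq.

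**Timing.** Protocol 7.1, footnote 1: "Intravenous infusion for 15min of the tracer starting 1h45min after the inhaled dose (time of the first inhalation"). The infusion ends at 2 h, which is the expected inhaled Tmax. Unlabelled plasma samples (Protocol 7.2.1.1) begin "15, 30, 60, 90 min, 2, 3.75, 5.75, 7.75, 9.75" h. The timing table in that section places the 2 h sample at end of infusion.

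**Derivation.** Protocol section 8 and SAP 9.1 compute F_inh as (AUC_inh × Dose_IV) / (AUC_IV × Dose_inh), with AUCs to infinity and the linear trapezoidal rule. AUC_inh, Cmax_inh and tmax_inh come from plasma non-radiolabelled CHF6001 as measured. Dose_IV is the total drug mass from syringe weights. Neither document mentions unlabelled drug from the infusion, and SAP section 12 declares no change from the protocol analysis.

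**The concern.** A microtracer design works by telling two simultaneous doses apart: label marks the IV drug, absence of label marks the inhaled drug. The second half of that is true only if the IV dose is essentially all labelled, and 18.5 µg carrying 18.5 kBq is far from that. Unlabelled IV molecules are chemically identical to inhaled ones, so no assay can separate them; only a derivation step can.

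At stake is the first-listed objective, absolute bioavailability. The error has the same sign in every subject, so neither averaging nor more subjects removes it. The peak measures are also exposed, because the infusion ends exactly when an unlabelled sample is taken and when the inhaled peak is expected.

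**Working it through.** **1. The protocol's own figures.** 18.5 / 3200 = 0.578%, so the stated bound of 0.6% is right. 3200 + 18.5 = 3218.5 µg. 500 nCi × 37 Bq/nCi = 18.5 kBq.

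**2. How much of the IV dose is labelled.** With one 14C per molecule and a half-life of 5730 years, the maximum molar activity is a physical constant, about 2.31 GBq/mmol (62.4 mCi/mmol). Labelled amount ≤ 500 nCi / 62.4 mCi/mmol = 8.0 nmol. Molecular weight is not in the documents, so a range is assumed:

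| Assumed MW | Labelled µg | Unlabelled µg | Unlabelled fraction u |
|---|---|---|---|
| 300 | 2.4 | 16.1 | 0.87 |
| 1000 | 8.0 | 10.5 | 0.57 |

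Full labelling would need a molecular weight near 18.5 µg / 8.0 nmol ≈ 2,300. More than one label per molecule would only raise u.

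**3. Effect on F_inh with exact AUCs.** Protocol 6.2.1 relies on linear PK, so contributions add. With clearance CL and total IV mass D:

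- AUC of unlabelled drug = (F × 3200 + u × D) / CL
- AUC_IV (as total IV mass) = D / CL
- F_obs = F + u × D / 3200

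Bias = 10.5/3200 to 16.1/3200 = 0.33 to 0.50 percentage points. It is additive, so its relative size is the bias divided by F:

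| True F (assumed) | Relative inflation |
|---|---|
| 5% | 6.6-10.1% |
| 10% | 3.3-5.0% |
| 30% | 1.1-1.7% |

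**4. Effect of the planned trapezoid.** Unlabelled samples fall at 1.5, 2 and 3.75 h. In the linear rule the 2 h value has weight (2 − 1.5)/2 + (3.75 − 2)/2 = 1.125 h, so a short end-of-infusion spike is spread over a long interval. The [14C] profile is sampled densely there and is not affected in the same way. Two-compartment simulation on the protocol's own times with u = 0.7 (assumed CL 20-40 L/h, central volume 10-60 L, plus a near one-compartment case with volume 300 L) gave 0.41-0.68 points, against 0.7 × 0.578 = 0.40 with exact AUCs. Other assumed two-compartment settings at u = 0.75 gave 0.44-0.90, against 0.43.

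**5. The 2 h sample, Cmax_inh and tmax_inh.** Illustrations from the same simulations at F = 10%, u = 0.7:

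| Assumed kinetics | True tmax | 2 h value | Cmax_inh | Observed tmax |
|---|---|---|---|---|
| Near one-compartment, ka 1.5/h | 2 h | +4.7% | +4.7% | 2 h |
| Two-compartment, half-life 17.0 h, ka 0.5/h | 1.5 h | +14.4% | +10.2% | 2 h |
| Same, ka 0.05/h (flat profile) | 11.75 h | +83.9% | +43.6% | 2 h |
| Two-compartment, half-life 17.6 h, ka 0.5/h | 0.5 h | +37.6% | 0 | 0.5 h |

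In every scenario the 2 h value rose proportionally more than F_inh. Whether Cmax_inh and tmax_inh change depends on where the true peak lies.

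**6. Is a correction feasible?** The unlabelled samples at 15, 30, 60 and 90 min precede the infusion. From 2 h to 241.75 h, each has a [14C] sample at the same clock time (infusion start + 15 min to + 240 h).

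**The case against.** The strongest reply is about materiality. The absolute bias is about half a percentage point, in an exploratory, descriptive study of 8 subjects with no test, interval or decision threshold attached to F_inh. If F is 30%, the relative error is 1-2%. The protocol says that the product was designed for low systemic exposure, but that is a design aim and supplies no F. This stands: the importance of the point is conditional on a low F_inh.

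A second reply is that isotopic composition and assay details sit in the separate pharmacy and analytical protocols, which are not available here. That stands for the exact value of u, but not for the principle: the activity-to-mass ratio in the protocol already implies that most of the dose is unlabelled for any ordinary small molecule.

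Three stronger readings are tempting and are not supported:

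- *That the 0.6% statement is an error.* It is correct and serves a safety comparison; it makes no claim about assay bias.
- *That 0.58 points is a ceiling.* It is one only with exact AUCs; the planned trapezoid can exceed it.
- *That the 2 h sample usually sets Cmax_inh, so Cmax_inh is inflated and tmax_inh is pulled to 2 h.* The documents give only an expected Tmax of 2 h. If the true peak is earlier and clearly higher, both are unchanged. No PK parameter in the documents supports a single figure for the Cmax effect.

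**Conclusion.** The concern holds in this form. As planned, F_inh includes an uncorrected contribution from unlabelled IV drug, always upward: 0.33-0.50 percentage points with exact AUCs, and about 0.4-0.9 points at u = 0.7-0.75 under the planned linear trapezoid and assumed two-compartment kinetics. It matters mainly if F_inh is around 10% or lower. Cmax_inh and tmax_inh may be distorted when the true peak is near 2 h or the profile is flat, but not when the peak is earlier and clearly higher.

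This rests on linear PK (stated in the protocol), a maximum of 62.4 mCi/mmol, an assumed molecular weight of 300-1000, [14C]-CHF6001 expressed as total IV drug mass, and assumed values of F and of the kinetics. It should be corrected because the direction is known and the remedy is cheap; it does not undermine the design.

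**What to change.** In Protocol section 8 and SAP 9.1:

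1. State the isotopic composition of the IV batch and obtain u, the unlabelled mass fraction, from its specific activity.
2. At each matched time from 2 h on, define C_inh = C_unlabelled − u × C_[14C]-CHF6001, with the [14C] concentration expressed as total IV drug mass, the same basis as Dose_IV. Leave the samples before the infusion as measured.
3. Derive AUC_inh, Cmax_inh, tmax_inh and F_inh from C_inh. Report the uncorrected values as a sensitivity analysis.
4. Say how the subtraction is handled when either concentration is below the limit of quantification or missing, and list the correction in SAP section 12 as a change from the protocol analysis.

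The subtraction also removes the end-of-infusion spike that the trapezoid would enlarge. The cost is one extra derivation and slightly more assay noise in the corrected concentrations. No new blood samples or assays are needed.

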## 6.2.2 Dosage

One single dose administration of CHF6001 will be given to all subjects, as follows:

### *CHF6001 DPI Inhalation:*

- 4 inhalations of CHF6001 800 $\mu$ g/20mg DPI NEXThaler® giving a total dose of 3200  $\mu$ g CHF6001

### *[ $^{14}\text{C}$ ]-CHF6001 IV infusion:*

- Detailed information on the process for formulation preparation are in the pharmacy protocol. The IV formulation will be administered intravenously as a single dose over 15 minutes, ending at the expected  $T_{\text{max}}$  of 2 h for the inhaled dose giving a total infused dose of 18.5 $\mu$ g and 500nCi (18.5kBq).

## 6.2.3 Administration

The treatment administration will take place at the clinical site in the morning of Day 1 of the treatment period, according to the instruction for use (provided in separate documents) and under the supervision of the investigator or his/her designee.

In the morning of Day 1, before treatment administration, restrictions related to the study drug administration will be applied, as reported in section [7.1.4](#).

### ***6.2.3.1 DPI administration***

The study medication will be administered using the DPI device.

For inhalation treatments, time 0 is defined as the moment when the first inhalation takes place. Subjects will take the medication in an upright position. Additionally, the subjects will be instructed to hold their breath for 10 secs following each inhalation and to wait 50 seconds before taking the next inhalation, in order to have 1 min between consecutive inhalations. A delay of  $\pm$  5 seconds will not be considered as a protocol deviation.

The dose counter of the NEXThaler® device should be inspected before and after each inhalation.

Detailed Instruction for use of the NEXThaler device for IMP use will be provided in a separate document.

Treatment evidence will be recorded in the eCRF and in the administration log, by the investigator or designee. Any issues occurred during the inhalations, evaluated in this sense by the investigator or designee, will be reported in the eCRF. An incorrect inhalation is defined as “a significant reduction of delivered dose that reaches the lungs based on investigator judgement”. Even if this is the case, no extra inhalations (i.e., more than the 4 inhalations required) will be administered.

In order to prevent any kind of contamination, the administration of the drug will take place in a ventilated room well separated from the blood sampling room. Subjects will remain in the room of administration only for the time strictly needed for the administration. Furthermore, during inhalation, subjects and assistant will wear special protective coats and gloves, which will be removed before entering the blood sampling room. The assistant administering the inhalations will not be allowed to participate in the blood sampling procedures on Day 1.

Clinical Study Code: CLI-06001AA1-02	Version No.: 1.0
EUDRACT No.: 2020-004201-31	Date: 19 October 2020

### **6.2.3.2 IV administration**

[C]-CHF6001 will be administered according to the pharmacy protocol to participants at the site by a 15 min intravenous infusion ending at the expected  $T_{max}$  of 2 h for the inhaled dose administered. Administration will be documented in the source documents and reported in the eCRF.

### **6.2.4 Subject Training**

#### **6.2.4.1 Training with In-Check DIAL**

At screening and on Day -1 and Day 1 pre-dose of the treatment Period, the In-Check DIAL will be used to train subjects to use the DPI inhaler correctly. In-Check DIAL is a PIF meter that simulates the internal resistance of the device, to enable the measurement of airflow as if the subject is using the device. The In-Check DIAL resistance selector will be aligned with the internal resistance of the NEXThaler® device. In order to ensure an optimum aerosol dispersion threshold, a PIF of at least 40 L/min is required. The optimal PIF is 60 L/min. Subjects who will reach the required PIF at the NEXThaler® setting, will be considered able to generate sufficient PIF for a correct inhalation with the NEXThaler®.

Following three successful inhalations with the In-Check DIAL device, the subjects will be asked to continue using the same inspiratory flow during drug inhalation. Detailed instructions for use of In-Check DIAL are reported inside the commercial package.

Subject will not be treated if the training is not completed with success. Training evidence will be recorded in the eCRF including the three “PIF” values.

#### **6.2.4.2 Training with DPI placebo**

At screening and on Day-1 and Day1 pre-dose of the treatment period, the correct use of the DPI device (NEXThaler®) will be explained to the subject according to the instruction for use (provided in separate documents).

Subject will be trained using placebo inhalers identical to the devices used for the administration of study drug. Therefore, the training will be done with DPI device, repeating inhalation for approximately 4 times.

At screening, and on Day -1 of the treatment period, the subject will receive a new training kit. The training kit dispensed at Day -1 will be used to follow the training procedure at Day -1 and Day 1 before the administration of the study treatment.

Subject will not be treated if the training is not completed with success. Training evidence will be recorded in the administration log and in the eCRF, by the Investigator or designee.

### **6.3 Packaging**

All investigational products will be prepared in accordance with Good Manufacturing Practices (GMP) as required by the current Good Clinical Practices (GCP). Chiesi Farmaceutici S.p.A. will supply the non-radiolabelled DPI material while [REDACTED] will supply the radiolabelled IV solution as described in the following sections.

### **6.3.1 Training Kit**

The training kits will be supplied to the Investigator as one DPI training box for each subject, containing one placebo DPI inhaler.

Clinical Study Code: CLI-06001AA1-02	Version No.: 1.0
EUDRACT No.: 2020-004201-31	Date: 19 October 2020

- Primary packaging: 1 labelled inhaler of CHF6001 Placebo NEXThaler® dry powder for inhalation
- Secondary packaging: 1 labelled pouch containing 1 labelled inhaler of CHF6001 Placebo NEXThaler®
- Tertiary packaging: Box containing 1 pouch containing 1 labelled inhaler of CHF6001 Placebo NEXThaler®

### 6.3.2 Treatment Kit DPI

Treatment kit will be supplied to the Investigator as one treatment kit for each subject.

- Primary packaging: 1 labelled inhaler of CHF6001 NEXThaler® dry powder for inhalation
- Secondary packaging: 1 labelled pouch containing 1 labelled inhaler of CHF6001 NEXThaler®
- Tertiary packaging: Box containing 1 pouch containing 1 labelled inhaler of CHF6001 NEXThaler®

### 6.3.3 Treatment Kit [14C]-CHF6001 IV infusion

The radiolabelled Drug substance (DS) will be provided by [REDACTED], [REDACTED] will manufacture the Drug Product (DP) for IV infusion supply straight to the clinic and the treatment kit will be composed by one glass vial containing the [C]-CHF6001 IV formulation. Further information can be found in the pharmacy protocol.

### 6.4 Labeling

All labeling will be in local language and according to local law and regulatory requirements and will be compliant with Annex 13 to the Volume 4 of the GMP.

### 6.5 Treatment allocation

All subjects will be administered one single dose (4 inhalations) of CHF6001 800µg/20mg DPI NEXThaler® according to a non-randomized, open-label design co-administered with an intravenous microtracer dose.

### 6.6 Treatment Code

No treatment code will be available since the study is performed according to a non-randomized design.

### 6.7 Treatment compliance

For each subject, the number of correct and incorrect inhalations taken during the treatment period will be recorded in the source documents and reported in the eCRF.

Clinical Study Code: CLI-06001AA1-02	Version No.: 1.0
EUDRACT No.: 2020-004201-31	Date: 19 October 2020

## **6.8 Drug Storage**

The Pharmacist/Investigator or designee will be responsible for the safe storage of all medications assigned to this study, in a secure place with restricted access, and maintained within the appropriate ranges of temperature.

**DPI training kits:** initial storage of pouched inhalers “Requires no special conditions”. Once removed from the pouch, the inhalers for training should be kept at ambient temperature but not above 30°C. At this temperature condition the residual shelf life will be six months (180 days). Therefore, the Pharmacist/Investigator at the site must write the use-by-date on the training kit labels once the inhalers are removed from the pouch. The use-by-date corresponds to the dispensing date plus 6 months. Please note that the use-by-date must not exceed the total shelf life of the product.

**DPI treatment kits:** initial storage of pouched inhalers: “Requires no special conditions”. Once removed from the pouch, the inhalers for treatment should be kept at ambient temperature but not above 25°C. At this temperature condition the residual shelf life will be six weeks (42 days).

All treatment and training kits, must be used by the subject only at the clinical site under Investigator/Pharmacist supervision.

**[C]-CHF6001 IV infusion treatment kits:** The solution for IV infusion will be stored between 2 to 8°C. Further information can be found in the pharmacy protocol.

